1.3.2. Japanese Phase 1 Study (Study DS3032-A-J103)

DS3032-A-J103 is a Phase 1 dose-ascending study of DS-3032b in Japanese subjects with advanced solid tumors or lymphomas. The objectives of the study were to evaluate the safety and tolerability of DS-3032b, assess the MTD or RP2D of DS-3032b, and evaluate the pharmacokinetics and pharmacodynamics of DS-3032b.

In this study, DS-3032b was administered once daily on Days 1 to 21, followed by a 7-day rest, in a 28-day cycle (qd 21/28 day schedule), starting from 60 mg and escalating through 90 mg and 120 mg, guided by mCRM with EWOC. As of 31 Oct 2016, a total of 18 subjects have been enrolled and treated in the study, and the study is currently underway. DLTs were reported in subjects treated at 120 mg, and the MTD for the qd 21/28 day schedule was determined to be 90 mg.

1.4. Known and Foreseeable Risks

DS-3032b was studied for potential toxicity in rats and dogs. In the 4-week repeated-dose toxicity study in rats, DS-3032b was well tolerated up to 1000 mg/kg (the highest dose tested). In the 3-month oral dose study, DS-3032b was well tolerated up to 300 mg/kg in males and 1000 mg/kg (the highest dose tested) in females. Weight loss and decreased food consumption were observed in males at 1000 mg/kg. In the 4-week repeated-dose toxicity study in dogs, DS-3032b was well tolerated at 3 mg/kg given as repeated oral doses. DS-3032b given as repeated oral doses of 10 mg/kg/day (the highest dose tested) was associated with moribund condition in the observation of clinical signs, with neutropenia, moderate to severe pancytopenia with bone marrow suppression, hemorrhage in multiple organs, and lymphocyte depletion in lymphoid organs. Effects on bone marrow and lymphoid tissues were predictable from pharmacology studies of DS-3032b. These results showed the primary target effects of DS-3032b on the hematopoietic/lymphoid system in dogs. In the 3-month repeated-dose toxicity study in dogs, DS-3032b was given as repeated oral doses of 3 mg/kg (the highest dose tested), and pancytopenia, suppression of the bone marrow and immune system, and hemorrhages in several organs were observed in 1 sacrificed male. In the surviving animals, a decrease in platelet counts was noted in males and females in the 3 mg/kg group.

Several reports are available for clinical studies using drugs that inhibit the MDM2-p53 interaction. According to published clinical data of MDM2 antagonists such as RG7112,¹⁴ RG7388,¹⁵ and SAR405838,¹⁶ adverse events (AE) of blood and lymphatic system disorders and gastrointestinal disorders have been reported.

In DS3032-A-U101, an overseas study in subjects with advanced solid tumors or lymphomas, treatment emergent adverse events (TEAEs) reported in more than 10% of a total of 69 subjects who have been treated as of 31 Oct 2016 were nausea in 47 subjects (68.1%), thrombocytopenia in 22 subjects (31.98%), platelet count decreased in 22 subjects (31.9%), fatigue in 35 subjects (50.7%), anaemia in 30 subjects (43.5%), diarrhoea in 27 subjects (39.1%), decreased appetite in 26 subjects (37.7%), white cell count decreased in 19 subjects (27.5%), leukopenia in 5 subjects (7.2%), neutropenia in 9 subjects (13.0%), neutrophil count decreased in 11 subjects (15.9%), vomiting in 20 subjects (29%), constipation in 16 subjects (23.2%), dysgeusia in 14 subjects (20.3%), cough in 14 subjects (20.3%), dyspnoea in 12 subjects (17.4%), headache in 11 subjects (15.9%), abdominal pain in 10 subjects (14.5%), dizziness and alopecia in 7 subjects (10.1%) each, and dry mouth and peripheral oedema in 9 subjects (13.0%) each.

Reported DLTs were Grade 4 thrombocytopenia and Grade 4 febrile neutropenia in 1 subject in the 240 mg qd group (21/28 day schedule), and Grade 3 anorexia, nausea, and vomiting in 1 subject and Grade 4 neutropenia and Grade 2 thrombocytopenia in 1 subject in the 160 mg qd group (21/28 day schedule). DLTs reported in the 120 mg qd group (21/28 day schedule) were Grade 4 thrombocytopenia in 1 subject and Grade 2 thrombocytopenia requiring dose interruption for more than 7 days in 1 subject. Grade 3 thrombocytopenia was also reported in 1 subject in the 90 mg qd 28/28 day schedule.¹² In DS3032-A-U102, an overseas study in subjects with advanced hematological malignant tumors, TEAEs reported in more than 10% of a total of 37 subjects who have been treated as of 17 Oct 2016 were nausea in 28 subjects (75.7%), diarrhoea in 21

subjects (56.8%), fatigue in 16 subjects (43.2%), vomiting in 13 subjects (35.1%), thrombocytopenia in 13 subjects (35.1%), anaemia in 12 subjects (32.4%), decreased appetite in 10 subjects (27%), hypotension in 10 subjects (27%), hypokalaemia in 9 subjects (24.3%), neutropenia in 9 subjects (24.3%), febrile neutropenia, pneumonia, hypomagnesaemia, and peripheral oedema in 6 subjects (16.2%) each, asthenia, dizziness, and dyspnoea in 5 subjects (13.5%) each, and pyrexia, dehydration, and hyperuricemia in 4 subjects (10.8%) each. DLTs reported in the 160 mg qd group (21/28 day schedule) were Grade 3 hypokalemia in 1 subject and Grade 3 diarrhea in 1 subject. DLTs reported in the 210 mg group (21/28 day schedule) were Grade 2 acute renal failure (less than 75% of the specified number of dosing days in Cycle 1), Grade 3 nausea and vomiting, and Grade 3 fatigue and anorexia in 1 subject each.¹³ In DS3032-A-J103, a Japanese study in subjects with advanced solid tumors or lymphomas, TEAEs reported in more than 10% of a total of 18 subjects who have been treated as of 31 Oct 2016 were nausea in 13 subjects (72.2%), decreased appetite in 11 subjects (61.1%), fatigue in 9 subjects (50%), white blood cell count decreased in 9 subjects (50%), hypoalbuminaemia in 7 subjects (38.9%), anaemia in 6 subjects (33.3%), platelet count decreased in 6 subjects (33.3%), constipation, diarrhoea, and vomiting in 5 subjects (27.8%) each, hyponatremia, ALT increased, and AST increased in 4 subjects (22.2%) each, thrombocytopenia, pyrexia, lymphocyte count decreased, neutrophil count decreased, and hypophosphatemia in 3 subjects (16.7%) each, and insomnia, cough, dry skin, proteinuria, and weight decreased in 2 subjects (11.1%) each. It is predicted from these results that DS-3032b may cause AEs of gastrointestinal disorders and blood and lymphatic system disorders. Patients treated with DS-3032b should therefore be closely monitored throughout the study period, and if any of these AEs occur, measures should be taken immediately.

Nonclinical data also suggest that coadministration of DS-3032b with CYP3A4/5 inhibitors or inducers may confound the metabolism of DS-3032b. Concomitant use of CYP3A4/5 inhibitors and inducers is therefore prohibited in this study.

2. STUDY OBJECTIVES

Primary Objective:

To evaluate the safety and tolerability of DS-3032b monotherapy administered as multiple doses and assess the MTD in Japanese subjects with relapsed or refractory AML.

Secondary Objectives:

- To evaluate the pharmacokinetics of DS-3032a
- To exploratively evaluate the antitumor effect of DS-3032b

Exploratory Objectives:

- To evaluate the pharmacodynamic effect of DS-3032b on macrophage inhibitory cytokine-1 (MIC-1) levels in serum
- To confirm if a *TP53* mutation is present or not using bone marrow and blood specimens
- To evaluate biomarker candidates related to the action mechanism of DS-3032b using bone marrow and blood specimens
- To assess the recommended dose in subsequent phases of development

3. STUDY DESIGN

This is a Phase 1, multicenter, open-label uncontrolled study. Combinations of doses and dosing schedules are shown in “[Figure 3.1 Combinations of Doses and Dosing Schedules](#).” Four dose-finding Subtrials (Subtrials A, B, C, and D) of DS-3032b will be conducted by fixing the dosing schedule. The study will be started from Subtrial A, and other subtrials will be conducted as necessary.

In Subtrials A, B, and D, the study drug will be administered once daily (qd) on Days 1 to 14, Days 1 to 7, and Days 1 to 21, followed by a 14-day, 21-day, and 7-day rest, respectively, in a 28-day cycle. In Subtrial C, the study drug will be administered once daily (qd) on Days 1 to 3, followed by a 11-day rest, in a 14-day subcycle, which will be repeated twice in a 28-day cycle.

Subjects must be hospitalized in Cycle 1, which is the DLT evaluation period. The number of treatment cycles will not be specified, and the study treatment for each subject will be continued unless the criteria provided in “[Section 5.6 Withdrawal Criteria](#)” are met.

The MTD will be determined for each subtrial (see “[Section 5.3.2 Definition of Maximum Tolerated Dose](#)”).

Figure 3.1: Combinations of Doses and Dosing Schedules

	Subtrial C	Subtrial B	Subtrial A	Subtrial D
Dose (mg)	160	B-3	A-3	D-3
	120	C-2	A-2	D-2
	90	C-1	B-1	A-1
	3/14 × 2	7/28	14/28	21/28
				Dosing schedule (day/day)

3.1. Starting Dose in Each Subtrial

The dose of DS-3032b for Cohort 1 in Subtrial A will be 90 mg (see “[Section 5.2.3 Rationale for the Dose and Regimen](#)”).

The starting dose in the subtrial that has a smaller number of dosing days than the subtrial in which the MTD has been determined will be equal to or lower than the MTD in the subtrial in which the MTD has been determined. For instance, when the MTD in Subtrial A is determined to be 120 mg, the starting dose in Subtrial B will be 120 mg or 90 mg.

The starting dose in the subtrial that has a greater number of dosing days than the subtrial in which the MTD has been determined will be lower than the MTD in the subtrial in which the MTD has been determined. For instance, when the MTD in Subtrial A is determined to be 160 mg, the starting dose in Subtrial D will be 120 mg or 90 mg. When the MTD has not been reached in Subtrial A, the starting dose in Subtrial D will be equal to or lower than the maximum dose used in Subtrial A.

3.2. Explorative Dose Finding in Each Subtrial

After confirming the DLT rate in Cycle 1 in each cohort in accordance with “Section 5.3.1 Definition of Dose-limiting Toxicities,” the dose for the next and subsequent cohorts will be determined, in consideration of the following i) and ii). As a rule, each cohort consists of 3 to 6 subjects, and if “Section 5.4 Enrollment of Additional Subjects” is applicable, enrollment of additional subjects will be considered.

- i) Recommended dose, guided by mCRM using a Bayesian logistic regression model (BLRM) incorporating the EWOC principle
- ii) Clinical evaluation of the toxicological profile and information on pharmacokinetics/pharmacodynamics (PK/PDy)

Rationale:

The study design was selected in reference to the “Guidelines for Clinical Evaluation of Anticancer Drugs.¹⁷” The Bayesian statistical analysis methods are specified in “Section 11.7 Details of Modified Continual Reassessment Method.”

4. STUDY POPULATION

4.1. Selection of Subjects

Subjects who satisfy all of the following inclusion criteria and do not meet any of the exclusion criteria are eligible for this study.

4.1.1. Inclusion Criteria

1. Provision of written informed consent for participation in this study.
2. Age ≥ 20 years old upon enrollment in this study.
3. Having AML (including those with a history of MDS) satisfying either of the following:
 - i) Have failed to achieve remission with at least 1 cycle of prior induction therapy
 - ii) Have relapsed after achieving remission with prior therapy
4. Those who appear unable to achieve persistent remission with standard treatment, who failed to complete potentially curative treatment, or who have no treatment options with expected therapeutic efficacy.
5. Eastern Cooperative Oncology Group (ECOG) performance status (PS) of 0 to 2 (refer to “[Appendix 2](#)”).
6. Having laboratory data satisfying all of the following criteria in the measurement within 14 days before enrollment in this study.

Laboratory Parameter	Requirement
AST	$\leq 2.5 \times$ the upper limit of normal of the center (ULN)
ALT	$\leq 2.5 \times$ ULN
Total bilirubin	$\leq 1.5 \times$ ULN
Serum creatinine	Creatinine clearance ≥ 60 mL/min, as calculated using the modified Cockcroft Gault equation* In case of creatinine clearance ≥ 50 mL/min and < 60 mL/min, as calculated using the above equation, the subject may be enrolled if the serum creatinine level is $\leq 1.5 \times$ ULN.
Prothrombin time-international normalized ratio (PT-INR)	$\leq 1.5 \times$ ULN
Activated partial thromboplastin time (aPTT)	$\leq 1.5 \times$ ULN

*: $([140 - \text{age (year)}] \times [\text{actual weight (kg)}]) / [72 \times \text{serum creatinine (mg/dL)}] (\times 0.85 \text{ [if female]})$

7. Able to take the following interval during the period from the last dose or last procedure of prior therapy to the start day of treatment with the study drug (study treatment) in this study.
 - i) Cytotoxic drugs: 2 weeks (48 hours for hydroxycarbamide used for the purpose of controlling the increase in white blood cells)
 - ii) Non-cytotoxic drugs: At least 5 times the half-life of the drug
8. Women of childbearing potential must have a negative pregnancy test at screening and must be willing to use highly effective birth control (eg, barrier contraceptives with spermicides, intrauterine device) during the following period: Upon enrollment, during the treatment period, and for at least 95 days after the last dose of DS-3032b. Women of childbearing potential are those in the period from first menstruation to menopause (no menstrual period for a minimum of 12 months). This, however, shall exclude permanently (surgically) sterile women.
9. Males must be surgically sterile or willing to use highly effective birth control upon enrollment, during the treatment period, and for at least 95 days after the last dose of DS-3032b. Male subjects may not donate their sperm during the study period and for at least 95 days after the last dose of DS-3032b.
10. Able to be hospitalized during the DLT evaluation period.

Rationale:

1. To ensure the eligibility of study subjects, and in consideration of ethics.
2. The lower limit of age is 20 years at which each subject can provide informed consent appropriately based on his/her own judgment.
- 3, 5, 10. To appropriately evaluate the safety of DS-3032b.
4. As recommended in the Guidelines for the Clinical Evaluation of Anticancer Drugs.¹⁷
6. To confirm that the subjects have adequate organ functions for appropriate evaluation of the subject's safety, as recommended in the Guidelines for the Clinical Evaluation of Anticancer Drugs.¹⁷
7. To confirm that the subjects are in a stable physiological condition at registration, as recommended in the Guidelines for the Clinical Evaluation of Anticancer Drugs.¹⁷
- 8, 9. Since an effect of DS-3032b on fetuses or infants cannot be ruled out. Breastfeeding women are not allowed to participate in this study independent of whether or not they temporarily discontinue breastfeeding.

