4.1.3.1. Flow of Subject Registration

After obtaining written informed consent from subjects, the investigator or subinvestigator will assign a subject identification code to each of the subjects. The investigator or subinvestigator will fill out the Subject Registration Form for subjects who are assessed to be eligible for the study among the above subjects and send it by fax to the sponsor.

The sponsor will confirm the eligibility of the concerned subjects against the inclusion and exclusion criteria for this study based on the information in the received Subject Registration Form. If there are any questions about the information in the Subject Registration Form, the sponsor will immediately contact the investigator or subinvestigator for confirmation. Subjects who are assessed to be eligible for the study by the sponsor will be registered in this study and assigned a subject number.

The sponsor will immediately fax the registration confirmation form with the result of eligibility assessment to the investigator; the confirmation form should include the date of registration, subject number, and dose of the study drug for subjects assessed to be eligible, and the fact that the subject is not eligible and the reason for subjects assessed to be ineligible. The investigator or subinvestigator will explain the reason for ineligibility to subjects who are assessed to be ineligible for the study by the sponsor.

Address for sending the Subject Registration Form (the sponsor's address)

Working hours: Monday to Friday, 9:00 to 17:30
(closed on Saturdays, Sundays, and public holidays)

FAX: PPD

TEL: PPD

[figure not shown]
The investigator or subinvestigator must not prescribe the study drug before registration of subjects.

If there is any subject who has provided informed consent, but is not registered in the study, the investigator or subinvestigator will record the reason why the concerned subject has not been registered in the medical record. Such a subject will not be included in the number of subjects enrolled in this study.

If a subject who has provided informed consent, but is assessed to be ineligible for the study at the time of eligibility confirmation and for whom a Subject Registration Form has not been faxed to the sponsor, is confirmed to satisfy the eligibility criteria at a later date, the investigator or subinvestigator may fax the Subject Registration Form to the

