5.2.2. Regimen

In Subtrial A, the study drug will be administered once daily on Days 1 to 14, followed by a 14-day rest, in a 28-day cycle (14/28 schedule). Each cycle is 28 days long.

[figure not shown]
Capsules with two different strengths will be used as the study drug (30 mg and 100 mg). As a rule, subjects will orally take the study drug once daily every morning under fasting conditions. Meal consumption should be avoided from 2 hours before dosing to 1 hour after dosing.

The first dose of the study drug will be started within 7 days of the day of registration. If the study treatment is started on Day 8 or later from the day of registration, the first dose of the study drug should be started only after the subject's eligibility has been confirmed again before the start of the study treatment (see "[Section 6.2 Study Procedures before Registration of Subjects](#)"). Day 1 of Cycle 3 and subsequent cycles may be rescheduled within + 3 days of the originally scheduled date. If the schedule of Day 1 is changed, all subsequent scheduled dates will be changed accordingly.

If a subject vomits after taking the study drug, it is not allowed to take another dose of the study drug on the same day.

Other dosing schedules (Subtrials B, C, and D) will be assessed if it becomes necessary in order to evaluate the safety of DS-3032b. Dosing schedules in each subtrial are shown in "[Figure 5.2-1 Dosing Schedules in Each Subtrial](#)."

Figure 5.2-1: Dosing Schedules in Each Subtrial

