6.2. Study Procedures before Registration of Subjects

The following examinations and assessments, etc. will be performed and the results will be recorded in the case report form.

Data collected before informed consent can also be used if they are obtained within the acceptable limit for each item.

If the study treatment is started on Day 8 or later based on the day of registration defined as Day 0, the patient's eligibility should be assessed again on the preceding day or the start day (before administration) of study treatment.

1. Items confirmed after informed consent obtainment but before the start of subject registration

- Date of informed consent to participate in this study
- Subject identification code
- Date of birth
- Sex
- Race
- Height
- Eligibility
- Medical history and complications

Symptoms that are expressed at the time of informed consent will be recorded as complications.

Regarding medical history, only symptoms/diseases that were cured at the time of informed consent and are considered necessary to be reported at the investigator's or subinvestigator's discretion will be recorded.

- Information on the underlying disease (AML)

Collect data on the date of the first diagnosis, the World Health Organization (WHO) classification, and the date of relapse.

- Prior therapy

The following items will be confirmed:

- Medications for AML: Drug name, stop date, best response, number of courses
- Radiation therapy for AML: Purpose, location, stop date, best response
- Hematopoietic stem cell transplantation: Details, date of transplantation
- Others: Details, stop date
- Assessment of SAEs

Information on SAEs that occur from after informed consent to before the first dose of the study drug will be collected. Information on non-SAEs is not subject to collection during this period.

2. Items performed within 14 days before the day of registration (screening tests)

*Performed on a day as close as possible to the day of registration

- Vital sign measurement

Axillary body temperature, pulse rate, and systolic and diastolic blood pressure will be measured at rest.

- Body weight measurement
- ECOG PS assessment

Subject's general condition will be assessed in accordance with the criteria provided in "[Appendix 2](#)."

- 12-lead ECG measurement (including evaluation of QTcF)

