A 12-lead ECG will be performed in the supine position after a 10-minute rest. Each measurement will be performed in triplicate at approximately 1- to 5-minute intervals.

- Laboratory tests

Laboratory Parameters	
Hematology test	Red blood cell count, reticulocyte ratio, hemoglobin, hematocrit, white blood cell count, white blood cell differential count (neutrophils, basophils, eosinophils, lymphocytes, monocytes), platelet count, PT-INR, and aPTT
Blood chemistry test	Total protein, albumin, total bilirubin, direct bilirubin, AST, ALT, ALP, BUN, serum creatinine, uric acid, glucose, electrolytes (K, Na, Cl, Ca, P, Mg), and CRP
Urinalysis	Occult blood, glucose, and protein

- Assessment of bone marrow findings

Assessment will be made based on bone marrow findings and peripheral blood results (neutrophil count, platelet count, and number of blasts) in accordance with “[Section 10.1 Definition of Efficacy Endpoints](#).”

It is desired to obtain bone marrow specimens by bone marrow aspiration and biopsy. If the investigator or subinvestigator considers that the antitumor effect of DS-3032b can be assessed adequately using specimens obtained by bone marrow aspiration only, bone marrow biopsy may be skipped.

- Pregnancy test

A urine or serum pregnancy test will be performed in female subjects.

A pregnancy test is not necessary in women who have been amenorrheic for at least 12 months after the last menstruation and who are considered to have no childbearing potential, or women who are not of childbearing potential after permanent surgical sterilization, etc. In this case, the information and reason will be recorded in the case report form.

A pregnancy test must be performed in women who have been amenorrheic for at least 12 months for medical reasons other than surgical sterilization (eg, medication) because they are considered to have childbearing potential.

3. Items confirmed within 90 days before the day of registration

- HBs antigen, HBs antibody, HBC antibody, HBV-DNA level, HCV antibody, HIV antibody

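### Read literally, inclusion criterion 8 ends childbearing potential after 12 months without a period, whereas sections 6.2 and 6.3 say medically caused amenorrhea does not end it

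*Combined protocol and SAP*

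**What the plan says.** Inclusion criterion 8 has identical wording in the protocol synopsis and in section 4.1.1. It requires women of childbearing potential to have a negative screening pregnancy test and to accept highly effective contraception from enrollment, through treatment, and until 95 days or more have passed since the final dose. It defines the group as follows: "Women of childbearing potential are those in the period from first menstruation to menopause (no menstrual period for a minimum of 12 months". The only exclusion it then states is permanent surgical sterility.

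The pregnancy-test items in 6.2 (before registration) and in 6.3.1, 6.3.2, 6.3.3 and 6.3.4 (Subtrials A to D) are more specific. They waive the test after 12 months of amenorrhea only if the woman is also judged to have no childbearing potential. They then require a test in women whose periods have been absent that long "for medical reasons other than surgical sterilization (eg, medication) because they are considered to have childbearing potential".

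The rationale given for criteria 8 and 9 is: "Since an effect of DS-3032b on fetuses or infants cannot be ruled out". Section 4.1.3.1 describes the sponsor's check at registration: "The sponsor will confirm the eligibility of the concerned subjects against the inclusion and exclusion criteria for this study".

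**The concern.** Criterion 8 explains menopause by duration alone. Sections 6.2 and 6.3 say that duration is not enough when the cause is medical. The protocol does not say which text prevails, and criterion 8 does not refer to 6.2.

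The pregnancy test itself is not at risk, because 6.2 and 6.3 require it for these women in their own right. Contraception is at risk. In the supplied text, the duty for women rests on criterion 8 only, so a site that applies that criterion as worded could decide that a woman with medication-induced amenorrhea need not use it. She could then conceive while exposed to a drug for which the sponsor does not rule out fetal harm.

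**Working it through.** No arithmetic on the design applies here, and the protocol gives no figure to reproduce. The check is to classify each type of woman under both texts, taking criterion 8 literally.

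| Woman | Criterion 8, read literally | 6.2 and 6.3 | Agree? |
|---|---|---|---|
| Still menstruating, not sterilized | Childbearing potential | Tested | Yes |
| Surgically sterile | None | Test waived | Yes |
| Natural menopause, 12 months or more | None | Test waived | Yes |
| Medically caused amenorrhea, under 12 months | Childbearing potential | Tested, since no waiver applies | Yes |
| Medically caused amenorrhea (not surgical sterilization), 12 months or more | None | Tested, and classed as having childbearing potential | **No** |

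Only the last row disagrees.

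**Where each text stands.** The definition without the medical-cause clause appears in 2 places (synopsis and 4.1.1). The clause appears in 1 + 4 = 5 places (6.2, and 6.3.1 to 6.3.4), each time under the pregnancy-test item.

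**Whether another part of the supplied text restores the contraception duty.**
- Criterion 9 covers men.
- Exclusion criterion 19 removes women who are already pregnant. It does not prevent later conception.
- The procedure lists in 6.4 and 6.5 contain no contraception item.
- Section 9.6 uses the same 95-day period, but for reporting pregnancies.
- Footnote g to the Appendix 1 schedules limits the pregnancy test to women of childbearing potential and does not define the term.
- Section 15.3 says subjects' responsibilities are explained at consent. The consent pages are not in the supplied text, so whether they cover contraception cannot be seen.

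None of the text that can be read places the duty on a woman whom criterion 8 has classified as past menopause.

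**How many women.** Section 11.6 plans 9 to 24 subjects of both sexes. The documents give neither the expected number of women nor the frequency of long medically caused amenorrhea. The affected number is a subset of the women enrolled and may be zero.

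**The case against.** The strongest reply is that the texts can be read together. The operative word in criterion 8 is menopause, and the 12 months only illustrates it. Amenorrhea caused by a drug is not menopause in ordinary clinical use, so such a woman stays within criterion 8 and 6.2 merely spells this out. This reading is reasonable, and the protocol taken as a whole points to contraception for these women. It does not remove the mismatch, because the only explanation criterion 8 gives is one that 6.2 treats as insufficient.

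The second reply is that safeguards make a miss unlikely. The screening pregnancy test in 6.2 belongs to the "Items performed within 14 days before the day of registration (screening tests" and so comes before enrollment. When the test is waived, "In this case, the information and reason will be recorded in the case report form". An investigator who follows 6.2 has already classed the woman as having childbearing potential, and would have to reverse that to exempt her under criterion 8. This stands as mitigation. The sponsor's check is weaker help: it is made against the criteria, which contain the looser definition. It uses a registration form whose content is not supplied, so whether it would catch the case is unknown.

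Third, sections 3 and 5.9 keep subjects in hospital during Cycle 1, which narrows exposure then. Overnight leave is possible, however, and hospitalization is not required in later cycles or after the final dose. Section 3 also says: "The number of treatment cycles will not be specified".

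A reader might infer three stronger things that the documents do not support:
- **That women will in fact be treated without contraception.** This depends on one contested reading of criterion 8, and the consent documents cannot be seen.
- **That the interval between scheduled pregnancy tests, or the time the duty runs past the Follow-up visit, measures the harm.** Both apply equally to every woman of childbearing potential, and correcting the definition changes neither.
- **That the trial's safety conclusions are affected.** Nothing in the DLT rules, the dose-escalation model or the analysis sets depends on this definition.

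**Conclusion.** The inconsistency is real and minor. It concerns one narrow group: non-sterilized women with at least 12 months of amenorrhea from a medical cause. For them, criterion 8 as worded can lift a contraception duty that 6.2's own classification implies they should have.

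Confidence is high that the texts differ. It is lower that any woman would be misclassified, since that requires a site to apply the definition literally and disregard 6.2. The conclusion that the duty appears only in criterion 8 holds for the supplied text without the consent pages. The number affected cannot be derived and may be zero. Dose escalation, DLT evaluation, the MTD and every analysis are untouched. The change is worth making because the possible harm falls on a fetus and the correction costs very little.

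**What to change.** Add one sentence to criterion 8, in both the synopsis and section 4.1.1, carrying over the rule in 6.2. For example: *A woman without periods for 12 months or longer because of a medical cause other than surgical sterilization, such as medication, is still regarded as having childbearing potential.* The sponsor may prefer to reuse its own wording from 6.2 so that all seven places match (2 + 5 = 7).

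No new test or visit is needed, and no statistical element changes. The downside is that a few more women may have to agree to contraception in order to be eligible.
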